## 12.2.1. Primary Safety Endpoint

The primary safety endpoint is freedom from procedure or device-related mortality.

CEC adjudicated data will be used to assess the safety endpoint.

The analysis cohort will be the catheterized cohort. The endpoint will be described by Kaplan-Meier statistics. The loglog transformed two-sided 95% confidence interval using the Peto standard error at 30 days will be presented. The primary safety objective will be met if the point estimate of the freedom from procedure or device-related mortality rate at 30 days post-procedure is equal to or greater than the performance target of 95%.

## 12.2.2. Primary Efficacy Endpoint

The primary efficacy endpoint is percentage of subjects with acceptable hemodynamic function composite at 6 months as defined by:

- Mean RVOT gradient as measured by continuous-wave Doppler echocardiography  $\leq 40$  mmHg
  - If a catheterization is performed for clinical purposes, the catheterization peak gradient measurement will supersede the continuous-wave Doppler echocardiography measurement and be used to support the primary endpoint. Acceptable hemodynamic function as measured by catheterization will be considered to be peak gradient  $\leq 40$  mmHg.

-AND-

- Pulmonary regurgitant fraction as measured by magnetic resonance imaging  $< 20\%$ 
  - If magnetic resonance imaging is contraindicated, a continuous-wave Doppler echocardiography measurement will be used to support the primary endpoint. Acceptable hemodynamic function as measured by continuous-wave Doppler echocardiography will be considered to be  $<$  moderate pulmonary regurgitation.

Core lab data will be used to assess the efficacy endpoint, with an exception in the case that a catheterization is performed to measure mean RVOT gradient, in which site reported data will be utilized.

---

 While the primary safety endpoint is measured at 30 days, primary objective analysis will be completed upon completion of the primary efficacy endpoint, which is measured at 6 months.

The analysis cohort for the primary efficacy endpoint will be the implanted > 24 hours cohort. The percentage of subjects with acceptable hemodynamic function at 6 months and a two-sided 95% Clopper-Pearson interval will be provided. The primary efficacy objective will be met if the point estimate is equal to or greater than the performance target of 75%.

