#### Implanted > 24 hours Cohort

The implanted >24 hours cohort consists of all subjects who have a Harmony TPV implanted which remains implanted for greater than 24 hours.

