#### Implanted > 24 hours Cohort

\_

<sup>1 Subjects must meet all inclusion/exclusion criteria to be eligible for implantation. However, it will not be considered a protocol deviation if study related testing (e.g., echo, CT cardiac angiography, or Screening Committee assessment) of a consented subject identifies implantation eligibility criteria that are not met.

Revision 5.1

Page 13 of 24

The implanted >24 hours cohort consists of all subjects who have a Harmony™ TPV implanted which remains implanted for greater than 24 hours.

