#### 7.9.2 Primary Efficacy Endpoint

The primary efficacy endpoint is percentage of subjects with acceptable hemodynamic function composite at 6 months as defined by:

- Mean RVOT gradient as measured by continuous-wave Doppler ≤40 mmHg
  - o If a catheterization is performed for clinical purposes, the catheterization peak gradient measurement will supersede the continuous-wave Doppler measurement and be used to support the primary endpoint. Acceptable hemodynamic function as measured by catheterization will be considered to be peak gradient ≤40 mmHg.

-AND-

- Pulmonary regurgitant fraction as measured by magnetic resonance imaging <20%

  - If magnetic resonance imaging is contraindicated, a continuous-wave Doppler measurement will be used to support the primary endpoint. Acceptable hemodynamic function as measured by continuous-wave Doppler will be considered to be < moderate pulmonary regurgitation.

-AND-

No prior Harmony valve reinterventions

The primary efficacy endpoint will be calculated using Core lab data, and analysis cohort will be the implanted >24 hours cohort. Analysis method details are provided in section 7.9.2.2.

Revision 5.1

Page 16 of 24

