#### 7.9.2.2 Data Collection and Analysis Methods

Core lab data will be used to assess the efficacy endpoint, with an exception in the case that a catheterization is performed to measure mean RVOT gradient, in which site reported data will be utilized. The analysis cohort for the primary efficacy endpoint will be the implanted > 24 hours cohort. The percentage of subjects with acceptable hemodynamic function at 6 month and a two-sided 95% Clopper-Pearson confidence interval will be provided. The primary efficacy objective will be met if the point estimate is equal to or greater than the performance target of 75%.

The efficacy endpoint will be assessed using the 6-month echo, diagnostic catheterization performed during the 6-month protocol window, and reintervention status through 6 months. If 6-month echo occurred prior to 6-month time window opening or missed, next available echo that is after the 6-month window opening will be used, unscheduled or 1-year echo, which ever came first. Tables below define success or failure for all possible scenarios. Only subjects whose procedure were 6 months prior will be included in the analysis. Modified TPV 25 subjects will be excluded from the primary analysis for PMA. The primary endpoint will be evaluated again when all subjects reach 6-month visit.

Previous Reinterventions or Diagnostic Catheterization Procedures			
	6-Month Echo Not Performed or Evaluable	6-Month Echo Acceptable Hemodynamics	6-Month Echo Unacceptable Hemodynamics
Any Harmony Reintervention Prior to 6-Month Window Closing	Fail	Fail	Fail
Diagnostic Cath Acceptable Hemodynamics Prior to 6- Month Window	Not Evaluable	Success	Fail
Diagnostic Cath Acceptable Hemodynamics During 6- Month Window	Success	Success	Success
Diagnostic Cath Unacceptable Hemodynamics Prior to 6- Month Window	Not Evaluable	Success	Fail
Diagnostic Cath Unacceptable Hemodynamics During 6- Month Window	Fail	Fail	Fail

Revision 5.1 Page 17 of 24

No Previous Reinterventions or Diagnostic Catheterization Procedures			
	6-Month Echo Not Performed or Evaluable	6-Month Echo Acceptable Hemodynamics	6-Month Echo Unacceptable Hemodynamics
Previous Echo Acceptable Hemodynamics	Not Evaluable	Success	Fail
Previous Echo Unacceptable Hemodynamics	Not Evaluable	Success	Fail

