#### 7.9.2.3 Sensitivity Analysis

For the primary efficacy endpoint, percentage of subjects with acceptable hemodynamic function composite at 6 months, the primary outcome will be calculated by excluding subjects whose 6-months echo data were not evaluable. Additionally, a sensitivity analyses will be calculated using the following criteria:

- worst-case outcome assumed all unable-to-be-assessed cases were failures
- best-case outcome assumed unable-to-be-assessed cases were successes
- last value carried forward outcome assumed all unable-to-be assessed cases were successes or failures using the last available information prior to 6-month window

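### A Harmony valve lost within 24 hours, or a failed implant attempt, drops out of the primary efficacy denominator, while removal after 24 hours counts as a failure

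*Protocol*

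**What the plan says.** Both documents assess primary efficacy in the same cohort. Protocol 12.2.2 states: "The analysis cohort for the primary efficacy endpoint will be the implanted > 24 hours cohort". SAP 7.9.2 repeats that the "analysis cohort will be the implanted >24 hours cohort". Protocol 12.1 defines it: "The implanted >24 hours cohort consists of all subjects who have a Harmony TPV implanted which remains implanted for greater than 24 hours". SAP 7.1.3 has the same definition, a "TPV implanted which remains implanted for greater than 24 hours".

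The decision rests on the point estimate alone (Protocol 12.2.2): "The primary efficacy objective will be met if the point estimate is equal to or greater than the performance target of 75" per cent. In addition, "a two-sided 95% Clopper-Pearson interval will be provided", but the interval plays no part in the decision. Protocol 12.2 says there is no hypothesis test and no sample size calculation.

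SAP 7.9.2 adds freedom from Harmony valve reintervention as a third component of success. The scoring table in SAP 7.9.2.2 has a row headed "Any Harmony Reintervention Prior to 6-Month Window Closing", and all three echo columns of that row read Fail. SAP 7.14 acknowledges that the CIP does not spell this component out, but says it was intended.

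SAP 7.9.2.3 plans three sensitivity analyses: worst case, best case and last value carried forward. Each reassigns only outcomes that could not be assessed; for example, "worst-case outcome assumed all unable-to-be-assessed cases were failures". None names a wider cohort.

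**The concern.** Membership of the primary efficacy cohort depends on something that happens after implantation: whether a Harmony valve is still in place past 24 hours. A valve removed at hour 30 is scored as a failure. A valve removed at hour 20, with none left in place, takes the subject out of the denominator. A failed implant attempt has the same effect. The SAP made reintervention a failure on purpose, yet the cohort definition removes the earliest complete device losses before that rule can apply.

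The 75% figure therefore describes subjects who kept a valve beyond the first day. A reader could take it as the success rate among everyone in whom the device was tried. With a bare point-estimate rule and about 40 subjects, a change of one or two in the denominator can decide whether the objective is met. An early explant in a surviving subject fails neither primary objective, because primary safety counts only procedure- or device-related death.

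**Working it through.** The plan has no sample size, power or derived figure to reproduce. The only stated number is the 75% target.

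**Inputs**
- N = 40 implanted in the pivotal cohort. Protocol 12 triggers the analysis on the first 40 implanted subjects, not 40 retained beyond 24 hours. Protocol 5 says that subjects who discontinue after implant are not replaced.
- N = 60 with the feasibility study (40 + 20). SAP 6 gives n = 20, and Protocol 12.2 includes those data in the primary objectives. Assumption: all 20 are implanted subjects.
- k = number of subjects whose valve is removed within 24 hours with no Harmony valve left. This is an assumption, because the documents give no figure; k = 0 to 4 is shown.
- All other subjects are taken as evaluable.

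**Formulas**
- Smallest passing count under the plan: r = ceiling of 0.75 × (N − k).
- Rate under the plan: r/(N − k). Rate with early removals counted as failures: r/N.
- Gap: r/(N − k) − r/N = [r/(N − k)] × k/N.

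**Results** (gaps from unrounded rates)

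| N | k | Plan | Early removals as failures | Gap (points) | 75% still met? |
|---|---|---|---|---|---|
| 40 | 0 | 30/40 = 75.0% | 30/40 = 75.0% | 0 | yes |
| 40 | 1 | 30/39 = 76.9% | 30/40 = 75.0% | 1.9 | yes |
| 40 | 2 | 29/38 = 76.3% | 29/40 = 72.5% | 3.8 | no |
| 40 | 3 | 28/37 = 75.7% | 28/40 = 70.0% | 5.7 | no |
| 40 | 4 | 27/36 = 75.0% | 27/40 = 67.5% | 7.5 | no |
| 60 | 0 | 45/60 = 75.0% | 45/60 = 75.0% | 0 | yes |
| 60 | 1 | 45/59 = 76.3% | 45/60 = 75.0% | 1.3 | yes |
| 60 | 2 | 44/58 = 75.9% | 44/60 = 73.3% | 2.5 | no |
| 60 | 3 | 43/57 = 75.4% | 43/60 = 71.7% | 3.8 | no |
| 60 | 4 | 42/56 = 75.0% | 42/60 = 70.0% | 5.0 | no |

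Exact 95% intervals for N = 40, k = 2 are 59.8 to 88.6% (29/38) and 56.1 to 85.4% (29/40). They overlap heavily, but the decision does not use them.

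**Away from the threshold.** Assume each retained valve succeeds with probability 80%, and hold k fixed. For N = 40, the chance of meeting 75% under the plan, against the chance with early removals as failures, is 0.759 v 0.759 (k = 1), 0.784 v 0.655 (k = 2), 0.809 v 0.533 (k = 3) and 0.832 v 0.401 (k = 4). For N = 60 and k = 2 it is 0.831 v 0.740.

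**Failed attempts.** If a further subjects have an attempt but no implant, the denominator becomes N + a. With k = 0 and a = 1 (assumed), 30/40 = 75.0% becomes 30/41 = 73.2%, and 45/60 = 75.0% becomes 45/61 = 73.8%.

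**The case against.** The cohort is prespecified, named and identical in both documents. Six-month hemodynamics in retained valves is a legitimate question, and the objectives are descriptive. The plan never presents the 75% figure as a rate among all attempts. All of this stands, and it is why the primary cohort need not change.

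A reader might also infer that early device losses disappear from the report. The documents do not support that. Technical and procedural success use the attempted implant cohort and are reported with the primary analysis, and procedural success requires device success at 30 days. SAP 7.11 also places device success in the attempted implant cohort, with a Kaplan-Meier estimate at 183 days; it requires the original device in place, no further device procedure and acceptable echo hemodynamics. SAP 7.13 lists device success for the pooled analysis. This narrows the gap but does not close it. None of these measures carries the 75% target, device success uses echo regurgitation instead of the MRI regurgitant fraction, and its final analysis is at 5 years.

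A reader might further infer that every reintervention on the first day escapes. It does not: the SAP table row has no 24-hour start, so a reintervention at hour 10 that leaves a Harmony valve in place keeps the subject in the cohort and scores Fail. Removal with immediate replacement by a second Harmony valve is ambiguous under the cohort definition.

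Nor is the worst-case analysis wrong for leaving early removals out. It deals with outcomes that could not be assessed, whereas early removals have known outcomes and raise a question about the cohort. SAP 7.9.2.3 does not restate its cohort; that it stays within the > 24 hours cohort is the natural reading, as a sensitivity analysis of that endpoint.

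**Conclusion.** The asymmetry is real and confined to two groups: subjects left without any Harmony valve within 24 hours, and failed implant attempts. No planned analysis sets these failures against the 75% target. Treating explant after 24 hours as Fail rests on the SAP's reintervention row and on Protocol 6.6, which links explant to reintervention; Protocol 12.2.2 alone does not say it.

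The size depends on counts that the documents do not give. With no early removals and no failed attempts there is no effect. At the minimum passing count and with no failed attempts, one early removal cannot reverse the conclusion; two can, at 40 or at 60 subjects. Per early removal the shift at the threshold is about 1.9 points at N = 40 and 1.3 at N = 60. The documents do not support a claim that the reported rate will be materially inflated, only that the plan would not show it if it were.

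**What to change.** Keep the > 24 hours cohort as primary. Add to SAP 7.9.2.3 a separate supportive analysis of the same composite in the attempted implant cohort, counting failed implants and explants within 24 hours as failures. Report it beside the primary figure and the 75% target, for both the pivotal and the pooled populations. State in SAP 7.1.3 whether a subject whose first valve is replaced at once by a second Harmony valve belongs to the > 24 hours cohort. Leave the worst-case analysis as it is, for outcomes that could not be assessed.

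The pivotal data are already needed for technical success, so the cost is one extra table row. The downside for the sponsor is that the supportive figure can only be equal to or less favourable than the primary one.

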## 12.3. Additional Outcome Measures

### Technical success at exit from catheterization lab/operating room (OR)

Technical success is defined as:

- No device- or procedural-related mortality, with
- Successful access, delivery and retrieval of the delivery system, and
- Deployment and correct positioning (including minor repositioning if needed) of the single intended device, and
- No need for additional unplanned or emergency surgery or re-intervention related to the device or access procedure

The analysis cohort for technical success will be the attempted implant cohort. The percentage of subjects with technical success will be presented. If an element of the composite is missing and available elements meet the success criteria, the subject will be excluded from the analysis.

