8. Subjects who are determined to be device candidates by the investigator are eligible for cardiac catheterization and Harmony TPV implantation. Implant attempt is considered the point at which the investigational product is introduced into the subject's body. Implantation procedures are described in the IFU document.

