#### Attempted Implant Cohort

The attempted implant cohort consists of all subjects who undergo catheterization and a Harmony TPV implantation was attempted (Harmony TPV is introduced into the subject's body).

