#### **Attempted Implant Cohort**

The attempted implant cohort consists of all subjects who undergo catheterization and a Harmony™ TPV implantation was attempted (Harmony™ TPV is introduced into the subject's body).

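### Technical and procedural success cannot register a failure that occurs before the valve enters the body, although their definitions name such failures

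*Protocol*

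**What the plan says.** Protocol 12.3 and SAP 7.11 (Outcome Measure #1) define technical success in the same way. Two of the required elements are "Successful access, delivery and retrieval of the delivery system" and "No need for additional unplanned or emergency surgery or re-intervention related to the device or access procedure". Absence of device- or procedure-related death is another.

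On the denominator, the Protocol states "The analysis cohort for technical success will be the attempted implant cohort", and the SAP uses the same cohort. Protocol 12.1 admits a subject to it when "a Harmony TPV implantation was attempted (Harmony TPV is introduced into the subject's body". SAP 7.1.3 sets the same condition.

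Procedural success at 30 days (Protocol 12.3; SAP 7.11, #3) combines device success at 30 days with freedom from a list of related serious adverse events. It is scored in the same cohort.

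Both documents also define a wider catheterized cohort: everyone taken to catheterization for possible implantation. The primary safety endpoint, all deaths and procedure-related adverse events use it (Protocol 12.2.1 and 12.3; SAP 7.9.1.2 and 7.10).

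Protocol 8.3, step 8, describes the attempt in different words: "Implant attempt is considered the point at which the investigational product is introduced into the" subject's body.

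**The concern.** Entry to the denominator depends on having got past part of what the outcome measures. Suppose a subject is judged a device candidate and taken to the catheterization laboratory, and venous access then fails before the valve enters. The definition calls that a technical failure, but the cohort rule removes the subject. The same applies to a procedure-related death, or to emergency surgery for an access complication, before valve entry.

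Both outcomes are brought forward to the primary-objective analysis (Protocol 12.3, Final Analysis; SAP 7.11). Technical success is also on the list to be pooled with the early feasibility study for the PMA (SAP 7.13). A reader of either percentage would reasonably take it to cover access from the start of the procedure. In a cohort of about 40, a few omitted subjects would visibly change it.

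**Working it through.** The documents give no expected rate, target or sample size for technical or procedural success, so there is no planned figure to reproduce. The check compares the definitions and then adds a simple illustration.

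**Step 1: which subjects can fail which element**

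- Access fails, or a named event occurs, after the valve has entered: the subject is in the attempted implant cohort and counts as a failure.
- The same happens before the valve has entered: the subject is in the catheterized cohort but not in the attempted implant cohort, and counts nowhere in either success rate.
- No section of either document adds the second group back as failures.

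**Step 2: what is reported for the second group**

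- Death: counted in the catheterized cohort, in the analysis of deaths and, if procedure- or device-related, in the primary safety endpoint.
- Procedure-related adverse event, such as a vessel injury: reported in the catheterized cohort.
- Access failure without an adverse event: appears at most in subject disposition (the flow diagram in SAP 7.1.1).

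**Step 3: size, under stated assumptions**

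Let n be the number attempted, s the number of successes among them, and k the number of failures before valve introduction.

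- Rate as planned: s / n, whatever the value of k.
- Rate with those failures counted: s / (n + k).
- Difference: (s / n) × k / (n + k).

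Inputs: n = 40 is an assumption taken from the up-to-40 implants in Protocol section 5, because the numbers attempted and catheterized are not given. The values 0, 2 and 4 for failures among the attempted, and k = 1 to 4, are illustrative and do not come from the documents. Anatomy-based stops are left out.

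| Failures among 40 attempted | As planned, any k | k = 1 | k = 2 | k = 3 | k = 4 |
|---|---|---|---|---|---|
| 0 | 40/40 = 100% | 40/41 = 97.6% | 40/42 = 95.2% | 40/43 = 93.0% | 40/44 = 90.9% |
| 2 | 38/40 = 95.0% | 38/41 = 92.7% | 38/42 = 90.5% | 38/43 = 88.4% | 38/44 = 86.4% |
| 4 | 36/40 = 90.0% | 36/41 = 87.8% | 36/42 = 85.7% | 36/43 = 83.7% | 36/44 = 81.8% |

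The drop runs from 2.2 points (36/40 against 36/41) to 9.1 points (40/40 against 40/44), or about 2.0 to 2.4 points per omitted failure. At k = 0 the two rates are equal.

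**The case against.** The strongest reply is that little is hidden. Deaths and procedure-related adverse events before valve entry are reported in the catheterized cohort. SAP 7.1.1 plans a flow diagram, SAP 7.4 promises the number of subjects in each analysis, and SAP 7.6 summarizes baseline data for the catheterized cohort. The gap between catheterized and attempted should therefore be visible. This stands, and it defeats any inference that harms go unreported. However, the reasons for non-attempt are not explicitly promised, and an access failure without an adverse event is never scored as a failure.

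A reader might also infer that the access element is met almost automatically. The documents do not support that. Failed delivery or retrieval, and access-related surgery after introduction, still count. Whether a failed 25 Fr access comes before or after valve introduction depends on when the valve is loaded. The implantation steps are in the IFU, which is blacked out in the public version. Only failures before any product enters are certainly excluded.

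The wording in Protocol 8.3 points the same way. The delivery system is also an investigational device (Protocol 6.4), so on that wording its entry alone would be an attempt, which makes the excluded group smaller. That calls for reconciliation and is not evidence of bias.

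The exclusion criteria cut both ways. Excluding anatomy that cannot take a 25 Fr system, and obstructed central veins, shows that access is a known hazard but should also make failure in the laboratory rarer.

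Finally, for 40/40 the exact 95% interval is 91.2% to 100%, so the rates for one to three omitted failures lie inside it. That is true, but such an interval describes chance variation and not the systematic removal of failures. The plan presents a percentage for technical success and states no interval.

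Success among attempted implants is a legitimate quantity, and it should stay.

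**Conclusion.** The point holds in a limited form. Both documents name elements of technical success that can fail before valve introduction, and both score the outcome in a cohort that such subjects never enter. Procedural success has the same gap. What is lost is the counting of these subjects as technical or procedural failures, chiefly access failures without an adverse event. Their deaths and procedure-related events are not lost.

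The size is unknown. Assuming 40 attempts, each omitted failure is worth about 2 percentage points, and there is no effect if none occurred. A reader might infer that the reported rates will be too high by a definite amount. The documents do not support that, because they give no number catheterized without an attempt.

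Severity is minor. Both outcomes are descriptive, neither has a performance target, and neither primary endpoint is analysed in the attempted implant cohort.

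**What to change.** In Protocol 12.3 and SAP 7.11 (#1 and #3):

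- Keep the percentage in the attempted implant cohort as planned.
- Add a second line in the catheterized cohort for technical success and for the whole procedural-success composite, so that the composite is not split across denominators. Count as failures the subjects in whom access failed, or a named event occurred, before valve introduction.
- List separately, with number and reason, the subjects whose catheterization was ended for anatomy before access for the delivery system was tried. Do not count them as failures, and state that they are outside the second-line percentage.
- Reconcile Protocol 8.3 with Protocol 12.1 and SAP 7.1.3, so that one event (entry of any investigational product, or entry of the valve) marks the attempt throughout.

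The cost is one more table row per outcome and a classified reason for each non-attempt, which sites may have to supply if it is not already collected. The catheterized cohort is already defined. The second-line rates may be slightly less favourable.
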